### 2.2 Randomization

Since the INTOMOB trial is a cluster RCT, only the wards (i.e., the clusters) have to be randomized. Ward randomization was done in a 1:1 ratio and generated shortly before start of the RCT by a statistician from CTU Bern (University of Bern, [name]). The statistician only received identifiers and not the actual names of the hospitals and wards in order to stay blind. Randomization was blocked with block size two and stratified by hospital to have the same ratio of intervention and control wards in each study center. Randomization was also stratified by ward size (<30 beds or  $\geq$ 30 beds). HCPs working on an intervention ward and participating patients admitted to an intervention ward receive the INTOMOB intervention. HCPs working on a control ward and participating patients admitted to a control ward receive the control procedure.

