## 2.8 Blinding

The intervention is partially blinded. Complete blinding is difficult due to the nature of the intervention, the communication between colleagues working on different wards (i.e., the clusters) and the rotation of the personal (mostly the physicians) across different wards. HCPs are informed in the e-learning part of the intervention, and orally during a presentation of the study, that they should avoid speaking about the intervention with colleagues of other wards.

Outcome assessment and data analysis is blinded. The primary outcome is assessed by phone by an investigator or one of her/his designees (study nurse, doctorand, PhD student, research fellow or medical student with completed GCP training) blinded to the intervention arm. The data analyst only receives identifiers and not the actual names of the hospitals and wards in order to stay blind. Moreover, the data analyst will be blinded to the randomization group.

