### 4.3 Estimands

#### 4.3.1 Primary outcome on the FAS

**Outcome of interest:** life-space assessment at 30 (+/-5) days

**Patient-set of interest:** full analysis set

**Handling of intercurrent events:** if the primary outcome is missing in more than 5% of patients, we will employ multiple imputation in the primary analysis and additionally perform an available case analysis as sensitivity analysis disregarding missing data.

**Population-level summary measure of outcome:** absolute difference with 95% confidence interval, computed using generalized estimated equations (GEEs) with Gaussian distribution, exchangeable correlation structure and robust standard errors with small sample correction.

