### 5.4 Baseline patient characteristics

Table 1 shows the list of baseline characteristics to be summarized. Continuous and count variables are presented as mean with standard deviation or median with quartiles, as appropriate. Categorical variables are presented as absolute and relative frequencies. Those variables will be presented by randomization group (intervention vs. control).

Table 1: Baseline table.

Description	Variable	Type
Age	age	Continuous [years]
Sex	sex	Categorical: female, male

Description	Variable	Type
Body mass index	weight_kg/height_cm	Continuous [kg/m  ]
Hospital	Hospital	Categorical: Inselspital, HFR, KSB
Number of hospitalizations in the last 180 days before admission	hosp_previous_n	Count
Support: home care	homecare	Binary: yes, no
Support: household help	household	Binary: yes, no
Support: mobility aid at admission	mobility_aid	Binary: yes, no
Life-space assessment		
Barthel Index (ADLs)	barthel_total	Continuous [range 0-100]
EQ-5D VAS	eq5d5l_vas2_uk_eng	Continuous [range 0-100]
DEMMI	demmi_score	Continuous [range 8-100]
Main diagnosis	hosp_cause	List of diagnosis categories
Number of medications at admission	med_n	Continuous

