## 6.2 Analysis methods

### 6.2.1 Primary analysis

The primary analysis will be an intention-to-treat analysis to compare the life-space assessment (LSA) between intervention and control groups at D30. LSA will be analyzed using GEEs with Gaussian distribution, exchangeable correlation structure and robust standard errors with small sample correction. This model accounts for the cluster design as well as for the small number of clusters and will be adjusted for the baseline LSA. The absolute difference between intervention group and control group will be presented with a 95% confidence interval (CI).

Continuous secondary outcomes will be evaluated likewise, adjusting for the baseline value if applicable. If outcome measures are non-normally distributed, we will apply an adequate distribution in GEE (e.g., gamma) or log-transform the outcome measure before analysis. Absolute differences between intervention group and control group will be presented with a 95% CI.

Binary outcomes will be analyzed using a GEE with a binomial distribution, a logit link, an exchangeable correlation structure and robust standard errors. Relative differences between groups will be presented as odds ratio with 95% CI.

Count outcomes will be analyzed using a GEE with a negative binomial distribution, a log link, an exchangeable correlation structure and robust standard errors. Relative differences between groups will be presented as rate ratio with 95% CI.

Time-to-event outcomes will be analyzed using a Cox regression model. To account for clustering, we will use shared frailties for clusters as well as cluster robust standard errors. Relative differences between groups will be presented as hazard ratio with 95% CI.

Categorical outcomes (discharge destination) will be analyzed using multinomial logistic regression with robust standard errors to account for clustering. Relative differences between groups will be presented as rate ratios with 95% CI.

Readmissions and emergency room visits will be analyzed as time-to-event outcomes, except if we notice that those outcomes often happen multiple times. In such case, we will analyze them as count outcomes.

Mortality and time to new institutionalization will be analyzed as time-to-event.

Falls will be analyzed as binary outcomes. If we notice that this outcome often happens multiple times, we will analyze it as a count outcome.

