### **6.4 Missing data**

If the primary outcome is missing in more than 5% of patients, we will employ multiple imputation in the primary analysis and additionally perform an available case analysis as sensitivity analysis disregarding missing data.

Multiple imputation will be via chained equations assuming missing data to be missing at random (MAR). Where endpoints are missing, each will be imputed separately to ensure robust imputation models. We will use all baseline variables (see table 1 in section 5.4) and outcome measures at all time points as predictors in the imputation models. Indicators for intervention and treatment will be included in the imputation model(s). Variables with more than 50% missing values will not be used for the imputation model. Binary variables with a frequency of less than 5% in one category will be omitted from the predictors, levels of categorical variables with a frequency of less than 5% in one category will be combined with another level in a sensible way. Continuous variables will be log-transformed if it improves normality (checked by Shapiro-Wilks test and QQ plots). If predictors are too highly correlated among each other, we will only consider the predictor which is more strongly correlated with the outcome. We will impute values using predictive mean matching for continuous and ordinal variables, logistic regression for binary variables, and a multinomial regression model for categorical variables with more than two levels. In total, fifty imputed data sets will be generated, which will be analyzed as described using Rubin's rules (Rubin 1987).

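### The imputation model in SAP section 6.4 does not name ward, the randomised cluster, so if imputation becomes primary the standard error may be modestly too small (minor)

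*SAP*

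**What the plan says.** Section 2.2 makes the ward the unit of randomisation: "only the wards (i.e., the clusters) have to be randomized". Section 2.3 gives 274 patients in 12 clusters. Section 6.2.1 analyses day-30 life-space with a Gaussian GEE adjusted for baseline, with "exchangeable correlation structure and robust standard errors with small sample correction", and presents this as the way the cluster design is respected.

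Section 4.3.1 sets the trigger: "if the primary outcome is missing in more than 5% of patients, we will employ multiple imputation in the primary analysis". The available-case analysis then becomes a sensitivity analysis.

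Section 6.4 describes the imputation in detail:
- Predictors: "We will use all baseline variables (see table 1 in section 5.4) and outcome measures at all time points as predictors".
- Design variables: "Indicators for intervention and treatment will be included in the imputation model(s".
- Method: "We will impute values using predictive mean matching for continuous and ordinal variables", with logistic and multinomial models for the other types and fifty data sets pooled by Rubin's rules.

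The only site variable in Table 1 of section 5.4 is hospital, with three levels ("Categorical: Inselspital, HFR, KSB"). Ward is not in the table.

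**The concern.** The analysis model relies on ward for its correlation structure and its robust variance, but the imputation model as written does not contain ward. A value imputed without ward is drawn towards what arm, hospital and the patient's own covariates predict, not towards the level of the patient's ward. Imputed patients therefore make the wards within a hospital look more alike than they are, and the GEE reads this as less clustering. The between-imputation part of Rubin's variance does not fully restore what is lost. The estimate itself is hardly affected; the width of its interval is.

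Section 6.4 fixes the imputation down to rare-category rules and the number of data sets, so this is a weakness in a stated rule and not a detail left to the protocol. The sentence on the two indicators needs correcting in any case, because a reader cannot tell what the first one is.

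**Working it through.** **Inputs from the SAP:** 12 wards in two arms (6 per arm), three hospitals, 274 patients (274/12 = 22.8, taken as 23 per ward), 50 imputations.

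**Assumed inputs (the SAP gives none):** ICC after baseline adjustment 0.02, 0.05, 0.10; day-30 scores missing in 10, 20, 30%. The small-sample correction is not named, so Kauermann-Carroll (KC) and Mancl-DeRouen (MD) are both shown. There is no plan figure to reproduce.

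**Step 1. Closed form on ward means, with hospital and all other predictors ignored (an upper bound on the loss).** Total variance is 1, ρ the ICC, p the missing share, m = 23, k = 6 wards per arm.
- Variance of an observed ward mean: v = ρ + (1 − ρ)/(m(1 − p))
- After imputation without ward: v* = (1 − p)²v + p/m
- Within-imputation variance of the arm difference: W = 2v*/k
- Between-imputation variance: B = 2p/(km(1 − p))
- Rubin total: T = W + (1 + 1/50)B
- True variance of the estimate: S = 2v/k + B/50

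For ρ = 0.10 and p = 0.20: v = 0.10 + 0.90/18.4 = 0.1489. v* = 0.64 × 0.1489 + 0.20/23 = 0.1040. W = 0.0347, B = 0.0036, T = 0.0384, S = 0.0497. Reported SE over true SD = √(0.0384/0.0497) = 0.88. With complete data the variance would be 2(0.10 + 0.90/23)/6 = 0.0464, so the pooled SE is √(0.0384/0.0464) = 0.91 of the complete-data SE. Imputation cannot add more information than the complete data hold, so that precision is not real.

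Reported SE / true SD, all cases:

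| ICC | 6% missing | 10% | 20% | 30% |
|---|---|---|---|---|
| 0.02 | 0.98 | 0.97 | 0.95 | 0.94 |
| 0.05 | 0.97 | 0.95 | 0.91 | 0.88 |
| 0.10 | 0.96 | 0.93 | 0.88 | 0.83 |

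**Step 2. Simulation with hospital in the imputation model.** 3,350 trials per scenario, 12 wards of 23, 50 imputations, missingness at random given baseline, baseline to day-30 correlation 0.5, no treatment effect. Imputation was single-level predictive mean matching on arm, hospital and baseline. Triples are 10/20/30% missing; type I error uses t with 10 degrees of freedom.

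| ICC | SE below available-case SE (KC) | SE / true SD, KC | SE / true SD, MD | Type I error, KC |
|---|---|---|---|---|
| 0.02 | none | 0.99/1.00/1.00 | 1.08/1.09/1.08 | 3.5 to 4.4% |
| 0.05 | 3/4/5% | 0.98/0.97/0.94 | 1.07/1.06/1.01 | 5.4/4.6/5.2% |
| 0.10 | 4/8/11% | 0.94/0.93/0.92 | 1.03/1.01/0.99 | 6.2/5.8/5.7% |

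The true SD was only 0.3 to 1.5% smaller than that of the available-case estimate. The GEE ward correlation fell to 85/74/66% of its complete-data value at ICC 0.05 and to 84/72/61% at ICC 0.10. Under MD, type I error was 2.6 to 4.3%. Monte Carlo error is about 1.2% on ratios to the SD and 0.4 points on type I error.

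**Step 3. More of the plan's predictors.** A discharge measure was added, and day-180 life-space observed in half of those missing day 30, both sharing the ward effect (favourable to the plan). SE / true SD with KC became 0.99/1.00/0.965 at ICC 0.05 and 0.97/0.98/0.98 at ICC 0.10, with type I error 4.3 to 5.4%. Under MD it was 1.05 to 1.10.

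**Step 4. Hospitals that also differ.** With an assumed between-hospital variance share of 0.03 and 20% missing, the KC ratio was 1.07 at ICC 0.05 and 1.00 at ICC 0.10.

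**Step 5. Independent checks of direction.** A separate 960-trial run with a KC-type variance put the single-level SE 2 to 6% below the available-case SE at ICC 0.05 (10 to 20% missing). At ICC 0.10 with 10% missing it was 4 to 5% below, and 0.97 of the complete-data SE. Ward-aware imputation did not fall below the complete-data SE, and type I error stayed at 4 to 6%. A smaller run (250 trials per scenario) found the SE without ward below the ward-aware SE in all 18 scenarios, by about 1 to 4% at 6% missing. With so few trials it supports the direction only.

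**The case against.** The strongest reply is that the plan would do little harm in practice. Section 6.4 calls for all Table 1 variables and outcomes at all time points, and predictors that share the ward effect carry much of the ward information; Step 3 is closer to the written plan than Step 2. Under Mancl-DeRouen, or at ICC 0.02 with Kauermann-Carroll, there is essentially no shortfall. The available-case analysis is already planned, and the mixed models of section 6.2.3, if fitted to the observed data, would keep the ward structure. All of this stands, and it sets the severity. It does not put ward into the imputation model, and those other analyses are only sensitivity analyses.

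A second reply is that the two indicators need not be one variable. Section 4.2.2 foresees patients changing between intervention and control wards, so assigned and received arm could both be meant; or the first word may stand for cluster. Either is possible. The first would still leave ward out. The second would put ward in without saying how, and that matters.

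A reader might infer that the primary interval will always be too narrow, or that the trial's type I error is materially inflated. The results do not support that: the shortfall needs an ICC of about 0.05 or more, a less conservative correction and weak predictors. A reader might also take the gap from two-level imputation as the size of the error. That would overstate it, because two-level imputation is itself slightly wide: at ICC 0.02 with KC the single-level SE is about right (0.99/1.00/1.00) and the two-level SE is 1.02/1.06/1.08 of the true SD.

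**Conclusion.** The point holds as a minor one. Section 6.4 omits the randomised cluster from an otherwise detailed imputation model, and one sentence in it is unclear on any reading. If imputation is triggered, ward correlation within hospitals is diluted. With ICC 0.05 to 0.10, 10 to 30% missing and a KC-type correction, the pooled SE is about 2 to 11% below the available-case SE with little true gain in precision, and near the low end when strong predictors share the ward effect. The shortfall is negligible at ICC 0.02 with KC and is absorbed by MD's conservatism; the SE is not understated when hospitals also differ. Type I error in simulation stayed at or below about 6%.

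These sizes rest on assumed ICC, missingness and correlations. The SAP refers to the protocol for the sample size assumptions, and the protocol was not available for this check. The direction for an ICC of about 0.05 or more does not depend on one simulation, since the closed form shows the same mechanism.

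**What to change.** Before database lock:

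1. State what the two indicators in section 6.4 are.
2. Replace that sentence with: *Treatment arm, and ward as a random intercept (two-level imputation), enter every imputation model.*
3. Amend the method sentence to match, for all variable types: two-level predictive mean matching for continuous and ordinal variables, and two-level models for binary and categorical ones. Otherwise the logistic and multinomial models stay single-level.
4. Do not enter ward as dummies. A separate simulation found that they over-widen the SE; its settings are not set out here, so only the direction is relied on.
5. Name the small-sample correction at the same time, since it decides which of the figures above apply.

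Blinding is no obstacle, because section 2.8 already gives the analyst coded wards: "The data analyst only receives identifiers and not the actual names of the hospitals and wards".

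**Cost:** text edits in section 6.4 and a two-level imputation routine. The ward variance is estimated from only 12 wards, so the interval becomes slightly conservative. Two-level predictive mean matching gave SE / true SD with KC of 1.02/1.06/1.08 (ICC 0.02), 1.02/1.05/1.04 (0.05) and 1.00/1.03/1.06 (0.10), with type I error 2.5 to 5.1%. The interval was 1 to 9% wider than the available-case one. With MD, type I error was 1.7 to 3.8%. Two-level imputation was not simulated with the discharge and day-180 predictors added, nor for binary or categorical variables, so its advantage under the plan's full predictor list is expected but not shown.

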## 6. Analysis

### 6.1 Outcome definitions

Table 2: Derivation of primary and secondary outcomes.

Outcome	eCRF sheet	Variable	Variable type	Derivation	Outcome type
Primary outcome: Life-space level or Life-space level for institutional setting at D30 [range 0-120]	Life-Space As- essment or Life-Space As- essment for in- stitutional setting (note: LSA and LSA-IS can be merged; same coding except with " is" in ad- dition [e.g., "ls1_yn_fu_is_d 30"])	ls1_yn_fu_d30	Binary: No, Yes	ls1_yn_fu_d30 * ls1_frequency_fu_d30 * [(2 if equipment=No and personhelp=No) OR (1.5 if equipment=Yes and personhelp=No) OR (1 if personhelp=Yes)] + 2 * ls2_yn_fu_d30 * ls2_frequency_fu_d30 * [(2 if equipment=No and personhelp=No) OR (1.5 if equipment=Yes and personhelp=No) OR (1 if personhelp=Yes)] + ... + 5 * ls5_yn_fu_d30 * ls5_frequency_fu_d30 * [(2 if equipment=No and personhelp=No) OR (1.5 if equipment=Yes and personhelp=No) OR (1 if personhelp=Yes)]***	Continuous
	ls1_frequency_fu_d30		Categorical: 1: <1x/week, 2: 1-3x/week, 3: 4-6x/week, 4: daily		
	ls1_equipment_fu_d30		Binary: No, Yes		
	ls1_personhelp_fu_d30		Binary: No, Yes		
	(Same variables with numbers from 2 to 5)				
Secondary outcomes					
1) Life-space level at D180				Same as primary outcome, with _d180 instead of _d30	
2) Activities of daily living (ADLs) at D30 and D180	ADLs (Barthel Index)	barthel_total_d30 / barthel_total_d180		Continuous [range 0-100]	Continuous
3) Instrumental activities of daily living (IADLs) at D30 and D180	IADLs (Lawton scale)	iadl_total_d30 / iadl_total_d180		Continuous [range 0-8]	Continuous

4) Quality of life at D30 and D180 (EQ-5D-5L VAS)	EQ-5D-5L	eq5d5l_vas2_uk_eng	Continuous [range 0-100]	Continuous
5) Depression at D30 and D180	Depression (PHQ-2)	depression_phq_2_d30/_d180	Binary (Yes/No)	Binary (yes/no)
6) Pressure ulcer at hospital discharge	Pressure ulcer	ulcer_yn_discharge	Binary (Yes/No)	Binary (yes/no)
7) Delirium during hospitalization	Delirium (Confusion Assessment method)	delirium_discharge	Binary (Yes/No)	Binary (yes/no)
8) Mobility at hospital discharge (DEMMI score)	Mobility: DEMMI	demmi_score_discharge	Continuous [range 0-100]	Continuous
9) Lower-limb muscle strength at hospital discharge	Muscle strength	strength_knee_discharge	Continuous 0-5 (from no activity to complete range of motion)	Continuous

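### The collinearity rule for the imputation model does not protect baseline LSA, the covariate of the primary model, and ignores whether the predictor it keeps is observed in the patients to be imputed

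*SAP*

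**What the plan says.** Multiple imputation is conditional but, once triggered, is the primary analysis (SAP 6.4): "If the primary outcome is missing in more than 5% of patients, we will employ multiple imputation in the primary analysis".

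The pool of predictors is wide: "We will use all baseline variables (see table 1 in section 5.4) and outcome measures at all time points as predictors in the imputation models". Table 1 in section 5.4 lists "Life-space assessment" among the baseline characteristics, and Table 2 in section 6.1 lists "1) Life-space level at D180" as the first secondary outcome, scored in the same way as the primary outcome. Both are therefore candidates for imputing D30 LSA.

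Two rules in 6.4 then thin the pool in ways that bear on LSA. One concerns availability: "Variables with more than 50% missing values will not be used for the imputation model". The other concerns collinearity: "If predictors are too highly correlated among each other, we will only consider the predictor which is more strongly correlated with the outcome". The only variables that 6.4 separately says will be included are the intervention and treatment indicators.

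In section 6.2.1 the primary GEE "will be adjusted for the baseline LSA".

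**The concern.** An imputation model should contain every variable of the analysis model it serves. If a covariate is left out, the imputed outcomes carry too little of its relation to the outcome, and the adjusted estimate inherits the distortion. Here the tie-break looks only at correlation with the outcome. A later score on the same scale may well win against one taken at admission, and the score that loses is the one the primary model conditions on.

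The rule also ignores where the kept predictor is observed. The 50% filter looks at each variable's overall missingness, not at whether it is missing in the same patients as D30 LSA. A patient lost before D30 may have no D180 score, while baseline LSA is collected at the start. The rule could thus keep a predictor that says nothing about the patients to be imputed and discard one that does.

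At stake is the primary estimate. Where loss depends on baseline LSA differently in the two arms, imputation without baseline LSA can be biased although the available-case model, which adjusts for baseline LSA, is not.

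**Working it through.** **Trigger.** 5% of the planned 274 patients is 0.05 × 274 = 13.7, so imputation becomes primary from 14 missing D30 scores. The SAP gives no figure that depends on the pruning rule, so there is none to reproduce. It also gives no LSA correlations, missingness rates or pattern of joint missingness. All such values below are assumptions.

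**Mechanism, limiting case.** Suppose the kept predictor is missing in the patients to be imputed and nothing else stands in for baseline LSA. Let m be the share missing in an arm, b the baseline slope, and g the mean baseline LSA of observed minus missing patients in that arm.

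- True arm mean = observed mean − m·b·g. The imputed arm mean is about the observed mean, so it is too high by m·b·g.
- The error in the arm effect is the difference between the arms' m·b·g. It cancels if loss depends on baseline equally in both arms. Otherwise it does not, and its sign follows the arm concerned.
- If loss is unrelated to baseline, the slope becomes about (1 − m)·b. With b = 0.75 and m = 0.15 this is 0.85 × 0.75 = 0.64.

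**Simulation A (SD units).** 274 patients, 1:1, 300 replicates, 8 imputations, chained normal regressions, ANCOVA on baseline LSA, clustering ignored. Assumed: true effect 0.30 SD; correlations baseline–D30 0.75, D30–D180 0.88, baseline–D180 0.80; D30 missing in 10% or 20%, depending on baseline; D180 also missing in 50%, 90% or 100% of those patients. D180 LSA correlated more strongly with D30 LSA than baseline LSA did in essentially all replicates. Monte Carlo SE of the effect was at most 0.006.

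| Imputation models | Dependence of loss on baseline | Effect (true 0.30) | Baseline slope (true 0.75) |
|---|---|---|---|
| Baseline LSA kept | either | 0.295–0.311 | 0.745–0.757 |
| Dropped from D30 model only | equal in arms | 0.294–0.304 | 0.713–0.739 (both rows) |
| Dropped from D30 model only | differs by arm | 0.307–0.344 | as above |
| Dropped from D30 and D180 models | equal in arms | 0.287–0.301 | 0.63–0.69 at 10%, 0.54–0.65 at 20% (all remaining rows) |
| Dropped from both, 10% missing | differs by arm | 0.350–0.405 | as above |
| Dropped from both, 20% missing | differs by arm | 0.392–0.489 | as above |

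With arm-differential loss and both models pruned, the error is 0.350 − 0.30 = 0.050 to 0.405 − 0.30 = 0.105 SD at 10% missing, and 0.392 − 0.30 = 0.092 to 0.489 − 0.30 = 0.189 SD at 20%.

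**Simulation B (LSA points).** Closer to the planned method: predictive mean matching, with two further baseline predictors kept. Assumed: SD 25, true effect 5 points, correlations 0.75 (baseline–D30), 0.85 (D30–D180) and 0.75 (baseline–D180), loss depending on baseline LSA in one arm only, clustering ignored. Shift from the full-data estimate with baseline LSA pruned, when 50%, 80% and 100% of patients missing D30 also lack D180:

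- 10% missing: 1.0, 1.4 and 1.7 points.
- 15% missing: 1.2, 1.9 and 2.4 points.
- Pruned from the D30 model only: 0.4–0.6 points at 10% and 0.5–1.0 at 15%.
- Baseline LSA kept: within 0.15 points. Available-case analysis: within 0.06.
- Equal dependence in both arms: at most about 0.2 points, although at 15% missing the slope still falls from 0.75 to 0.61–0.66.

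**Wider range of correlations.** With correlations of 0.75 to 0.90 and 15% missing, the shift was about 1.4–2.5 points with both models pruned and one-arm dependence, about 0.3–1.2 with the D30 model alone pruned, at most about 0.3 with equal dependence, and within about 0.15 with baseline LSA kept.

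**The case against.** The case against is substantial and limits the point in several ways.

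- **The rule has a trigger.** Nothing is pruned unless two predictors are judged too collinear; stronger correlation with the outcome only decides which one stays. A reader might infer that baseline LSA will be dropped. The SAP does not support that: it gives neither a cut-off nor the correlation. At a correlation of 0.6 the two scores share 0.6² = 36% of variance, and the rule would hardly fire. Only high-correlation scenarios are relevant, so only those are used here.
- **Joint missingness is not documented.** A reader might infer that patients without a D30 score usually lack D180 as well. D30 and D180 are separate visits (section 2.7), and a patient can miss one and attend the other. That some lack both is plausible, but it is an assumption.
- **Bias in the arm effect is conditional.** It needs loss that depends on baseline LSA differently by arm. The simulations in points take a strong form of this, dependence in one arm only. The missing-at-random assumption in 6.4 allows it, but nothing shows it will occur.
- **Chaining softens the harm.** Missing D180 scores are themselves imputed, so baseline information can reach D30 LSA through the D180 model. This reduces the shift but does not remove it. Section 6.4 imputes each endpoint separately, so the rule could also remove baseline LSA from the D180 model, where it competes with D30 LSA.
- **The planned model is richer than the simulated ones.** Other Table 1 variables and outcomes could recover part of what is lost, so the figures indicate order of size only.
- **There is a partial safeguard.** The available-case analysis that 6.4 requires alongside imputation would help reveal a distortion of this size. It would not say which result is right.

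All of this stands. None of it supplies the missing exemption.

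**Conclusion.** The point holds as a gap in a rule. Section 6.4 permits removal of the primary model's own covariate from the imputation that becomes the primary analysis above 5% missing, and no other provision of the SAP prevents it. Whether it would happen cannot be told from the document.

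The size is conditional. The figure of about 1.4 to 2.5 LSA points rests on assumed correlations of 0.75 to 0.90, 15% missing, pruning in both the D30 and D180 models, loss tied to baseline LSA in one arm, and no clustering. Its sign is arbitrary. With the same dependence in both arms the arm effect is practically unaffected, though the baseline slope is still weakened.

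Severity is minor to moderate: the harm needs several conditions together and the available-case analysis would help expose it, but it concerns the primary endpoint and is avoidable at almost no cost.

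**What to change.** Add to section 6.4: *The arm indicator, baseline LSA and any other covariate of the analysis model being fitted are always kept in the imputation model. The collinearity rule applies to auxiliary variables only; between correlated auxiliaries, the one observed in more of the patients to be imputed is preferred.*

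A numerical cut-off for excessive correlation would also help, so that the choice is not left until the data are seen. The protection of analysis-model covariates is the essential part.

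The cost is SAP wording only, with no new data. Keeping baseline LSA beside D180 LSA leaves some collinearity in the model, but in the simulations above the estimates stayed close to the full-data or true values when it was kept.

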## 2. Study Methods

### 2.1 Trial design

The INTOMOB RCT is a multicenter, cluster, randomized, controlled, superiority trial conducted in three hospitals in Switzerland, with a 180-day follow-up. The intervention is partially blinded. Outcome assessment and data analysis are blinded. Hospital wards are randomized in a 1:1 ratio to either intervention or control arm. Patients admitted to an intervention ward receive the intervention, while patients admitted to a control ward receive standard of care.

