### 2.3 Sample size

See section 5.1 of the protocol, under “Sample size calculation for the RCT”. The calculated sample size includes a total of 274 patients (137 in each arm, and in 12 clusters in total).

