## 4. Statistical Principles

### 4.1 Confidence intervals and *P* values

All effect measures will be accompanied by a two-sided 95% confidence interval. All applicable statistical tests will be two-sided and will be performed using a 5% significance level.

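### With 12 wards, the primary GEE names no reference distribution and the cited pooling rule ignores the ward count, so the 5% level is not secured

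*SAP*

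**What the plan says.** SAP 2.1 randomizes wards, not patients: "Hospital wards are randomized in a 1:1 ratio to either intervention or control arm". SAP 2.3 gives the size as 274 patients, "137 in each arm, and in 12 clusters in total". SAP 4.1 sets the error rate for every test: "All applicable statistical tests will be two-sided and will be performed using a 5% significance level". It also requires two-sided 95% intervals, but names no distribution from which their multiplier is taken.

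The primary model (SAP 4.3.1 and 6.2.1) is a Gaussian GEE with exchangeable correlation and robust standard errors, adjusted for baseline LSA. The standard errors carry a small-sample correction that is not named. Of this model SAP 6.2.1 says: "This model accounts for the cluster design as well as for the small number of clusters".

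SAP 6.4 makes multiple imputation part of the primary analysis once more than 5% of primary outcomes are missing, and fixes the pooling: "In total, fifty imputed data sets will be generated, which will be analyzed as described using Rubin's rules (Rubin 1987". SAP 6.7 allows Stata or R and names no routine or df option. The SAP nowhere states df, a t or normal reference, or a multiplier, either for a single data set or for the pooled result.

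**The concern.** With few clusters, a robust GEE has two separate problems. The sandwich standard error is too small on average, and even a corrected one is itself estimated from few units, so the test statistic has heavier tails than the normal. A small-sample correction of the standard error addresses the first problem. The second needs a t-type reference, or a correction strong enough to make up for its absence. The SAP specifies the first without naming it and leaves the second open.

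The imputation branch then cites a pooling rule whose df contain no term for the complete-data df. Taken literally, it treats the complete-data analysis as having unlimited df, although only 12 units were randomized.

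At stake are the width of the primary confidence interval and the false-positive rate of the primary test. The choice of correction and reference would also remain open until the data are in hand.

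**Working it through.** **Inputs from the SAP.** 12 wards and 274 patients (2.3); 1:1 allocation by ward (2.1), hence 6 against 6; two-sided 5% (4.1); m = 50 and the pooling citation (6.4). The figure in question is the nominal 5%. The sample size itself cannot be reproduced, because SAP 2.3 leaves its inputs to the protocol.

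**Assumptions not in the SAP.** λ, the between-imputation share of the pooled variance, 0.05 to 0.20; ICC 0.01 to 0.10; 0 to 20% missing.

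**Step 1: df of the arm effect.** 12 wards − 2 arms = 10. The t critical value is 2.228, against 1.960 for the normal. If the statistic follows t on 10 df but is read at 1.96, the level is P(|t₁₀| > 1.96) = 7.8%. With 9 df it is 8.2%.

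**Step 2: pooling df.**

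- Rule as cited: ν₁₉₈₇ = (m − 1)/λ² = 49/λ².
- Barnard-Rubin with ν_com = 10: ν_obs = [(10 + 1)/(10 + 3)] × 10 × (1 − λ) = 8.46 × (1 − λ), and ν_BR = 1/(1/ν₁₉₈₇ + 1/ν_obs).

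| λ | ν₁₉₈₇ | Critical value | ν_BR | Critical value | Ratio |
|---|---|---|---|---|---|
| 0.05 | 49/0.0025 = 19,600 | 1.960 | 8.0 | 2.304 | 1.18 |
| 0.10 | 49/0.01 = 4,900 | 1.960 | 7.6 | 2.327 | 1.19 |
| 0.20 | 49/0.04 = 1,225 | 1.962 | 6.7 | 2.384 | 1.22 |

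Patient-level complete-data df (274 − 3 = 271) would not help, since the multiplier would still be near 1.97. Only ward-based df change it.

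**Step 3: simulated level under the null.** All runs use a Gaussian exchangeable GEE with a baseline covariate, 12 wards, and m = 50 where values are imputed. Setting A has 12 equal wards of 23, ICC 0.01 and 0.05, and 10–20% missing (10% only where ward is in the imputation model). Setting B, in brackets, has random ward sizes summing to 274, with ICC 0.01–0.10 for complete data and 0.05 with 10–20% missing. The Monte Carlo standard error in setting A is about 0.3–0.5 points. K is the number of wards and p the number of regression parameters.

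Rejection rate (%) with a normal reference (complete data) or the 1987 df (imputed):

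| SE correction | No missing data | Imputed, ward in imputation model | Imputed, ward left out |
|---|---|---|---|
| K/(K − 1) | 9.1–9.9 | 6.0–7.6 | 7.8–9.7 |
| K/(K − p) | 6.3–6.8 | 4.1–5.7 | 6.0–7.4 |
| Kauermann-Carroll | 7.6–8.3 (8.2–8.7) | 5.1–6.5 (7.1–7.3) | 6.9–8.9 (8.9–10.1) |
| Mancl-DeRouen | 5.4–5.7 (5.7–6.3) | 3.6–4.8 (4.9–5.2) | 5.0–6.4 (6.1–7.3) |

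The last column matters because the predictors listed in SAP 6.4 (Table 1 variables, outcomes, intervention indicators) include hospital but not ward.

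**Step 4: level with ward-based df.** With no missing data and t on 10 df, Kauermann-Carroll gives 4.7–5.1% (5.3–5.7%) and Mancl-DeRouen 2.9–3.7% (3.7–4.2%). Imputed and pooled with Barnard-Rubin df, the results over both imputation models in setting A are 2.5–4.6% for Kauermann-Carroll (3.1–4.9%) and 1.6–3.3% for Mancl-DeRouen (2.0–3.8%).

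**The case against.** A reader might infer a stronger point: that imputation switches the primary interval to 1.96 standard errors, so the 5% level fails. The documents do not support that, for three reasons.

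- The SAP never writes 1.96 or a normal reference. The multiplier follows from the cited rule taken literally. The citation may be meant only as the general source for combining imputed results, with df left to the software.
- Imputation does not create the gap. SAP 6.2.1 states no t reference for the unimputed GEE either. With a normal reference and complete data the level is already 5.4–9.9%. Pooling with ward in the imputation model gives lower rates than complete data in every row of the second table.
- SAP 6.4 has each imputed data set analyzed by the model already described, so the small-sample correction carries into every within-imputation variance. With Mancl-DeRouen, which the text allows, the level is near 5%.

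Two further points are fair. The highest rates partly reflect the omission of ward from the imputation model, which is a separate matter from the pooling df. And the narrowness of the interval (1.96/2.30 to 1.96/2.38, that is 15–18%) is measured against Barnard-Rubin df, which are themselves somewhat conservative here, so it overstates the shortfall from nominal coverage.

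What remains is that the plan claims to handle the small number of clusters, but fixes neither the correction nor the reference distribution, and cites a pooling rule with no place for the ward count.

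**Conclusion.** The concern holds as a level that is not secured, in SAP 6.2.1 and 6.4 together. It does not hold as a statement that the level is lost, or that pooling is the cause. Depending on a correction the SAP does not name, the actual two-sided level is about 4–7% (Mancl-DeRouen) or about 5–10% (Kauermann-Carroll or K/(K − 1)), with or without imputation. The upper end also includes the effect of leaving ward out of the imputation model.

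The df arithmetic depends only on m = 50, the 12 wards and the assumed λ. The error rates rest on more assumptions: the ICC, ward sizes and missingness given above, and for setting A also a baseline–outcome correlation of about 0.5, outcomes missing completely at random, normal-model imputation instead of predictive mean matching, and no adjustment for strata. Severity is should-fix: it concerns the primary interval and P value, but some permitted choices already come close to 5%.

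**What to change.** In SAP 6.2.1 (and 4.3.1), name the small-sample correction together with its reference distribution, for example Kauermann-Carroll standard errors with t on wards minus 2 = 10 df for the interval and P value. In SAP 6.4, replace the bare 1987 citation with Rubin's rules using Barnard-Rubin df, complete-data df = 10, and a t-based 95% interval and P value.

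This takes about two sentences of text and one line of code, and should be settled before database lock so that neither choice can follow the results. The statistical cost is an interval about 14% wider than at 1.96 without imputation (2.228/1.960 = 1.14) and about 18–22% wider with it, and some loss of power. The imputed test is then slightly conservative, about 3–5% with Kauermann-Carroll. Pairing the same df with Mancl-DeRouen would be more conservative, about 2–4%, so the correction and the df should be chosen as a pair.
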